8.2.1. Imputation of Missing Efficacy Data

In general, there will be no imputation of missing data in efficacy analyses other than the primary endpoint (overall survival).

Imputation of the primary endpoint may depend on the date of the first occurrence of an event associated with the endpoint. When the event has yet to occur the analysis will nonetheless require an analytical date be available for the analysis. These are known as censored or truncated dates. A censored date is the date of the most recent assessment for the event for a subject for which the event of interest has yet to occur and for which additional time may lead to observation of the event of interest. A truncated date is the date of a competing event that precludes the observation of the event of interest. The distinction between designating an analytical date as censored or truncated will depend on the purpose of the analysis and will be designated for each analysis. For example, if death is the event of interest and a subject is still alive and being followed for the date of death then the date last known alive is a censored date, whereas the date a subject withdraws consent for continued follow-up of vital status (a competing event) is a truncated date. The nature of the competing event will dictate whether the

competing event is permanent. For example, the date of death for a subject who has withdrawn consent may later become known passively from governmental death records.

Dates associated with the primary endpoint with missing day of the month will be completed by imputing the missing day of the month as the 15th day of that month, provided another date to be used in the computation of an interval is not in the same month. If the day of the month is missing and the other date is in the same month, then the missing day of the month will be taken as half the distance to the beginning or end of the month (depending on expected sequence). If both dates to be used in the computation of an interval are missing day of the month then an interval of 15 days (plus or minus) will be used.

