Dates associated with the primary endpoint with both month and day of month missing will be imputed as July 1 of the known year provided another date in the same year is to be used in the computation of an interval. If both the month and day of the month are missing and another date in the same year is to be used in the computation of an interval, then the missing date components will be taken as the half the distance from the other date until the beginning or end of the year (depending on expected sequence). If both dates to be used in the computation of an interval are missing both month and day of the month then an interval of 180 days (plus or minus) will be used.

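### The year-only date rule for overall survival has lost a *not*: two sentences conflict for same-year dates, and different-year dates have no rule

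*SAP*

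**What the plan says.** SAP 8.2.1 gives three sentences for a primary-endpoint date that lacks both month and day.

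1. July 1 of the known year is the value to use, on a stated condition: "provided another date in the same year is to be used in the computation of an interval".
2. The next sentence opens with the same condition, "If both the month and day of the month are missing and another date in the same year is to be used" for that purpose, and gives a different value: "the missing date components will be taken as the half the distance from the other date" to the start or end of the year, according to which date should come first.
3. The last sentence is for two incomplete dates: "If both dates to be used in the computation of an interval are missing both month and day of the month", the interval is set to 180 days.

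The preceding paragraph of 8.2.1 deals with a missing day only. Its default is "imputing the missing day of the month as the 15th day of that month". That default carries the condition "provided another date to be used in the computation of an interval is not in the same month". Where the other date does fall in that month, half the distance is used.

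SAP 3.2.1 defines overall survival (OS) as the end date minus the randomization date plus 1. SAP 8.2.2 applies the 8.2.1 rules in the primary survival analysis.

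**The concern.** Sentences 1 and 2 share one condition and give two answers. The opposite condition, a year-only date with the other date complete and in a different year, gets no answer, because sentence 3 needs both dates to be incomplete. July 1 makes sense as a default only in that uncovered case.

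At stake is the derivation of the primary endpoint. A rule of this kind should give one survival time per man, fixed before unblinding. An imputed calendar date can also affect whether a death is counted. SAP 8.1.1 censors at a cutoff date, and SAP 12 bases the definitive analysis on the data as they stood when the required number of deaths was first reached.

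A smaller, separate gap is that neither the day-only nor the year-only rule refers to the date last known alive.

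**Working it through.** **Logic.** The two rules of SAP 8.2.1 side by side, with the other date complete:

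| Missing part | Other date in a different period | Other date in the same period |
|---|---|---|
| Day only | 15th of the month | Half-distance |
| Month and day, as written | No rule | July 1 *and* half-distance |
| Month and day, with *not* restored | July 1 | Half-distance |

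Restoring the word makes the two rules match. No other text fills the gap. SAP 6.2.2 uses July 1 as a plain default, but for prostate cancer history. SAP Appendix C covers adverse events and medications.

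**Same-year dates.** OS = imputed date − randomization date + 1 (SAP 3.2.1). The year is taken as 2013 for illustration. Half-distance is the whole number of days in half the interval from randomization to 31 December.

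| Randomized | OS, July 1 sentence | OS, half-distance sentence |
|---|---|---|
| 1 February | 150 + 1 = 151 | 166 + 1 = 167 |
| 2 July | −1 + 1 = 0 | 91 + 1 = 92 |
| 1 September | −62 + 1 = −61 | 60 + 1 = 61 |
| 1 October | −92 + 1 = −91 | 45 + 1 = 46 |
| 1 December | −153 + 1 = −152 | 15 + 1 = 16 |

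Under the July 1 sentence, any randomization after 1 July gives OS of zero or less. In a 365-day year July 1 is day 182, so this is 365 − 182 = 183 days, or 50.1% of the year.

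**How deaths divide between the two cases.** No figure in the plan depends on this rule. The planning hazard was reproduced first: ln 2 / (22/12) = 0.3781 per year and exp(−3 × 0.3781) = 32.2%, both as in SAP 4.1.1. Exponential survival was then simulated for 800 men under the accrual pattern of SAP Appendix B (19-month ramp, 30 months in total), cut at the 534th death. There were 400 replicates per setting, with hazard ratio 1 or 0.68 without delay. The calendar start of accrual is an assumption and was varied over the year.

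- About 74% to 80% of deaths fall in a different calendar year from randomization.
- Of the same-year deaths, about 21% to 32% are in men randomized in the second half of the year. Multiplying within settings, the smallest product is 0.223 × 0.209 = 4.7% of all deaths and the largest is 0.253 × 0.295 = 7.5%.

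These are shares of all deaths. They are not the frequency of year-only dates.

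**After the correction.** The shortest different-year OS is for randomization on 31 December with death imputed to the next July 1: 182 + 1 = 183 days in a non-leap year. Same-year OS is at least 1 day, so no value is zero or negative.

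**Last known alive.** Even the corrected rule can place death at 1 July for a man known to be alive on 30 December of that year, 182 days later. The day-only rule can place it at the 15th for a man known to be alive on the 31st, 16 days later.

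**The case against.** The strongest reply is that this is a one-word slip with an obvious repair. The missing-day rule shows the intended structure, sentence 2 already covers same-year dates and respects sequence, and July 1 is the only value the section offers for a different-year date. A careful programmer would probably get it right. That stands and limits the severity. It does not remove the defect, because the current text still gives two answers in one case and none in the other.

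A reader might infer that the plan will place deaths before randomization. The documents do not support this without qualification. It happens only if sentence 1 is followed over sentence 2, and only for a man randomized after 1 July who dies in the same calendar year. Such deaths fall within about six months of randomization, largely in the Treatment phase with its frequent visits (Protocol 14.1), where a date known only to the year is least plausible apart from early dropouts.

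A reader might also take the 74% to 80% as the share of men affected. It is not. The rule matters only when a death date is known only to the year, and the documents give no count of these. Collection procedures suggest few: vital status sweeps with each data monitoring committee meeting (Protocol 5.1), pursuit of death certificates (Protocol 5.4) and six-monthly survival contacts (Protocol 7.5). SAP 8.2.1 does expect that some deaths may be learned passively from government records, so the number need not be zero.

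Nor do the documents support an inference of bias between arms. The imputation rule makes no reference to arm.

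**Conclusion.** Wrong as written, minor severity. The same-year conflict and the different-year gap follow from the text alone and need no assumption. For one man the two sentences can differ by months: 61 − (−61) = 122 days for a 1 September randomization. The effect on the logrank test cannot be computed without a count of year-only dates. It is probably small, on the assumption that such dates are rare. The absence of a last-known-alive limit is a distinct refinement, worth up to about six months (year-only) or about two weeks (day-only) in an affected man's survival time.

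**What to change.** In the July 1 sentence of SAP 8.2.1, change the condition "provided another date in the same year is to be used in the computation of an interval" by inserting *not* after the word *is*, so that July 1 applies only when the other interval date is in a different year. Leave the half-distance sentence for same-year dates as it stands.

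Separately, add one sentence covering both the day-only and the year-only rule: an imputed death date may not be earlier than the date last known alive, and must stay within the known month or year. The limit should read *on or after*. Using the day after last contact could move a date known to be in March to 1 April, or one known to be in 2012 to 2013, and would exclude death on the day of last contact. No separate limit at randomization is needed once *not* is restored.

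The cost is one word and one sentence, settled before unblinding. Design, alpha and sample size are unchanged.

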8.2.2. Survival Analysis Method

Imputation of missing date parts will follow the rules previously specified. Competing events for death are “definite” lost to follow-up and withdrawal of consent for continued vital status assessments. Both of these competing events are subject to revision for an individual subject with the passage of time.

The primary analyses will be performed on the ITT set and will analyze subjects according to the randomized arm. The primary analysis will be repeated on the FAS as a sensitivity analysis.

The primary test of each endpoint will consist of a stratified logrank test for the test of the null hypothesis (STRATA <stratification-variable> / TEST=LOGRANK;). See [Section 4.2](#) for the definition of the stratification variable. The significance of the logrank test will be assessed by referring the one-sided stratified logrank test P_1 to 0.0125, and the comparison will be said to meet statistical criterion if $P_1 < 0.0125$.

Notes:

- These analyses must be stratified: Anderson et al. 2006.
- When there are competing events then censoring competing events provides a between-arm test of the event of interest: Prentice et al. 1978.

The hazard ratio for each comparison will be estimated using stratified (STRATA <stratification-variable>;) proportional hazard regression with the specification of ties handled by the exact method (TIES=EXACT option on MODEL statement). Two-sided 95% confidence interval will be reported in order to maintain consistency with the reporting of estimates from other prostate cancer studies.

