The significance levels to be used for the analyses associated with these two comparisons will protect the overall study type I error probability to be one-sided 0.025 or less. The possibility of delayed vaccine effect is taken into account in computing the required number of deaths, (as modeled from the randomized Phase 2 trial). The projected trial size is 400 subjects per arm (approximately 1,200 subjects) with at least 85% power, and the final analyses will be event-driven and take place when 534 deaths have been realized for the comparisons involving all subjects randomized (Arm V+G versus Arm P, and separately Arm V versus Arm P).

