4.1.4. Power and Significance Level

The trial is planned so that a between-arm logrank test for all subjects will have the target power. The target power taking into account the possibility of a delay in effect is specified to be 85% or greater. The two comparisons will be done with Bonferroni correction to the overall type I error probability so that the type I error probability for each will not exceed one-sided 0.0125 ($=0.025/2$).

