4.1.5. Number of Subjects and Required Number of Deaths

The number of subjects per arm is set to be 400 (Approximately 1200 total subjects). The accrual rate distribution is 19 months of linear ramp up followed by 11 months of constant rate of accrual (2.5 years to accrue approximately 1200 subjects). Note: The accrual distribution assumptions have been updated from the assumptions used originally to plan this trial and are based on current accrual experience. The table below has been revised to reflect these new accrual assumptions and there is no material modification to power, hypothesized hazard ratio, or any other important aspect of the trial design. As expected, the revised computations do change the projections for time to analysis. The assumptions used in [Table 1](#) match the assumptions used in the interim analysis planning computations outlined on pages 23 and 24. Please see [Appendix B](#) for more detail around the 19 month linear ramp followed by 11 months constant rate of accrual.

The trial is planned as an event driven trial. Simulation is used to compute the required number of deaths after setting other specifications. [Appendix A](#) to this document describes the simulation methodology. [Table 1](#) below shows the results of the simulations.

Table 1: Simulation Results

Case #	Delayed Effect	Specified # deaths	Time to specified deaths (y)	1-sided type I error probability estimate (%)	Power estimate (%)	Critical hazard ratio
1	No	340	3.4	1.17	90.2	0.784
2	Yes	340	3.3	1.13	44.5	0.784
3	Yes	534	5.1	1.23	86.1	0.823
4	No	534	5.2	1.12	98.8	0.823

Notes:

- Simulations are for the comparison of one of the experimental arms to control arm, that is, 800 subjects, 400 per arm, accrued over two years, with a 19 month ramp time followed by a constant accrual rate for 11 months (2.5 year total accrual).
- 10,000 replications for each case.
- Significance level is one-sided 0.0125. The column “One-sided type I error probability estimate (%)” from the simulations should be approximately 1.25%. Target power with delayed effect is 85% or more.
- The control arm data are generated under the exponential distribution with 22 month median survival.
- The experimental arm data under the specific alternative and when delayed effect (if applicable) are generated so that hazard rates are equal for 4 months (hazard ratio = 1), followed by a linear transition over next 4 months to target hazard ratio of 0.68, with hazard ratio = 0.68 from 8 months onward.

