8.2. Primary Analyses (Survival)

The survival outcome from subjects in each experimental arm, Arm V and Arm VG, will be compared separately to the survival outcome from subjects in the control arm, Arm P. If either of these comparisons passes the statistical criterion specified previously, then the trial will be regarded as having met the statistical criterion for success. This section defines the statistical method and criterion for each of these survival analyses.

The survival analysis objective is to ascertain whether the survival time distribution for subjects randomized to the experimental arm is consistent with longer survival as compared to subjects randomized to the control arm. All randomized subjects will be included in the primary survival analysis according to the randomized arm (intent-to-treat).

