9.7. Immune Monitoring

Immune Monitoring data will be presented in the data listings.

10. Quality of Life

Subject-reported quality-of-life (QOL) data will be presented in the data listings.

11. Radiology

Radiological assessments will be performed at Screening, Week 13, Week 25 EOT, and at the 6-month long term follow-up visit.

Radiology data will be presented in the data listings.

12. Interim Analysis

This section describes the interim analysis plan (IAP) to be executed by the independent statistician and assessed by the DMC. The specific IAP results are closed to the sponsor unless one of the criteria are met, and even then the DMC will use its discretion regarding the communications of results to the sponsor, with patient safety balanced against benefit being the primary concern. This IAP consists of the ability to detect early evidence of efficacy and also futility.

The statistical computations used to devise this IAP take into account the possibility of a delayed effect of the same magnitude as used to plan the trial size but the statistical tests will ignore the possibility of delayed effect because there cannot be certainty that a delayed effect exists. Stated another way, the statistical tests to be done as specified in the IAP are optimal in cases where the hazard ratio is proportional; the alternative is intractable because it would be to use parametric statistics in a situation where the underlying form of the failure-time distribution is not known. Thus, if the possibility of a delayed effect were not taken into account and it actually exists then the IAP would have lower power to detect early efficacy than anticipated because early events would not be discriminatory for efficacy, and a conclusion of futility would have increased power because early events would be give a false signal about lack of efficacy. By contrast, if the possibility of delayed effect were taken into account when a delayed effect does not exist then the IAP will have greater power than anticipated to detect early efficacy whereas futility would have diminished power than anticipated.

The IAP is designed so that interim analyses for a comparison are to be executed at 40%, 60%, and 80% information times, corresponding to 214, 321, and 427 deaths, with the final analysis at 534 deaths as previously discussed.

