The one-sided significance criteria to be used for early detection of efficacy analyses are 0.000135, 0.00147, 0.00501, respectively, with the adjusted final analysis to use 0.01063. These significance levels were computed using SAS PROC SEQDESIGN as one-sided O'Brien-Fleming boundaries with an overall one-sided type I error probability of 0.0125. Following is the SAS code used to compute these intervals.

```
proc seqdesign boundaryscale=pvalue;  
  design  
    nstages=4  
    info=cum(0.4 0.6 0.8 1)  
    method=obf  
    alt=upper  
    stop=reject  
    alpha=0.0125  
  ;  
run;
```

The early detection of efficacy is to use the same statistical testing methodology as specified for the primary analysis. The statistical characteristics for the interim analysis event-driven time-points and significance levels are computed using simulations. The simulation methodology for delayed effect is described in [Appendix A](#). The following table shows the statistical operating characteristics of this plan based on 10,000 simulation replicates. For example, when the alternative hypothesis is true (average hazard ratio = 0.68) then at the second interim analysis is projected for 3.2 years following the start of randomization and the estimated cumulative probability of rejecting the null hypothesis is 0.1571 (with confidence interval as shown). Also shown is the largest hazard ratio found for which the null hypothesis was rejected (rej HR), showing that at this interim analysis a hazard ratio less than or equal to 0.716 will pass the criterion for early efficacy (an estimate of the critical hazard ratio). Please note that these simulations are consistent with the targeted overall one-sided type I error of 0.0125: for analysis 4 (“#” column) the proportion of trials rejected (“rejected” column) under the null hypothesis (row with “null” in the “hyp” column) is 0.0127, and is close enough to 0.0125 considering computations were done using simulation.

Statistical Operating Characteristics of the Interim Analysis Plan

Simulation estimates (cumulative, # replications = 10000):

#	events	hyp	time	test	rejected	95% CI	rej HR		
1	214	null	2.5	futile	0.0771	0.0719 to 0.0825	≥ 1.212		
				superior	0.0000	0.0000 to 0.0004	≤ 0.000		
		alt	2.5	futile	0.0054	0.0041 to 0.0070	≥ 1.216		
				superior	0.0065	0.0050 to 0.0083	≤ 0.603		
				null	3.0	futile	0.2297	0.2215 to 0.2381	≥ 1.090
						superior	0.0013	0.0007 to 0.0022	≤ 0.712

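### SAP 8.2.2 sets the primary survival criterion at one-sided 0.0125, while SAP Section 12 and protocol 9.8 set 0.01063 for the same final analysis; nothing says which governs

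*SAP*

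**What the plan says.** The overall limit is in the protocol synopsis under Statistical Methods: the significance levels "will protect the overall study type I error probability to be one-sided 0.025 or less". SAP 4.1.4 splits it equally between the two comparisons (V+G versus P, V versus P), so that "the type I error probability for each will not exceed one-sided 0.0125". Protocol 9.4 does the same. Success on one comparison is enough (SAP 8.2): "If either of these comparisons passes the statistical criterion specified previously, then the trial will be regarded as having met the statistical criterion for success".

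Two places then give a decision level for the final test.

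- SAP 8.2.2 specifies the stratified logrank test and judges it by "referring the one-sided stratified logrank test P_1 to 0.0125, and the comparison will be said to meet statistical criterion" when P_1 is below 0.0125. It mentions neither interim analyses nor Section 12.
- SAP Section 12 plans analyses at "40%, 60%, and 80% information times, corresponding to 214, 321, and 427 deaths, with the final analysis at 534 deaths". The one-sided efficacy levels are "0.000135, 0.00147, 0.00501, respectively, with the adjusted final analysis to use 0.01063". Protocol 9.8 repeats the four levels and gives their purpose as holding 0.0125 per comparison.

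The notes to Table 1 in SAP 4.1.5 also use the unadjusted level: "Significance level is one-sided 0.0125".

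**The concern.** In SAP 4.1.4 and protocol 9.4, 0.0125 is the total type I error allowed to a comparison. In SAP 8.2.2 the same figure is the nominal level of a single test. The two uses agree only if the comparison is tested once. With three earlier chances to reject, using the full 0.0125 again at the last look spends more than was allotted.

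SAP 8.2 says that it defines the criterion for the survival analyses, and its reference to a criterion already specified points back to Section 4.1.4, not forward to Section 12. A programmer working from 8.2.2 would code 0.0125. The independent statistician working from Section 12 would use 0.01063.

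A final P value between 0.01063 and 0.0125 would be a success under one section and a failure under the other, and the choice would be made after the result was known. The secondary endpoint, alive without event (AWE), inherits the problem: SAP 8.3 makes its test depend on the survival comparison meeting its criterion and reuses the survival significance levels.

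**Working it through.** **Inputs.** Alpha per comparison 0.0125 (SAP 4.1.4). Looks at information fractions t = 0.4, 0.6, 0.8 and 1.0, that is 214, 321, 427 and 534 deaths (SAP Section 12). O'Brien-Fleming boundary, four stages, one-sided, early stopping to reject (the SEQDESIGN code in Section 12). Allocation 1:1:1 with one control arm (SAP 4.2).

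**Step 1: reproduce the plan's levels.** The boundary is z_k = c/√t_k, with c chosen so that the total null crossing probability over the four looks is 0.0125. Recursive numerical integration gives c = 2.3034, so z = 3.642, 2.974, 2.575 and 2.303. The upper-tail probabilities are 0.000135, 0.00147, 0.00501 and 0.01063. All four match Section 12 and protocol 9.8.

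**Step 2: change only the last level.** The interim levels stay as planned.

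| Look | Nominal level | First crossing at this look (null) | Cumulative |
|---|---|---|---|
| 214 deaths | 0.000135 | 0.000135 | 0.000135 |
| 321 deaths | 0.00147 | 0.001385 | 0.00152 |
| 427 deaths | 0.00501 | 0.004013 | 0.00553 |
| 534 deaths, Section 12 | 0.01063 | 0.006969 | 0.01250 |
| 534 deaths, SAP 8.2.2 | 0.0125 | 0.008607 | 0.01414 |

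The last row replaces the row above it. The ratio 0.01414/0.0125 = 1.13, an excess of 13% per comparison. The exact death fractions (214/534 and so on) give the same 0.01414.

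**Step 3: the whole trial.** The Bonferroni bound is 2 × 0.01414 = 0.0283, against 2 × 0.0125 = 0.025. The shared control makes the two statistics positively correlated (0.5 under the null with equal arms), so the bound overstates the error. Simulating both four-look sequences with a common control (30 million replicates, standard error 0.00003) gives:

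- final level 0.01063: 0.0233
- final level 0.0125: 0.0262

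**Step 4: does futility stopping offset it?** Treating futility as binding at the critical hazard ratios in the Section 12 table (1.212, 1.090, 1.023) leaves 0.0141 per comparison and 0.0262 overall. It does not.

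**Step 5: what it means on the hazard ratio scale.** Critical HR = exp(−2z/√534), with √534 = 23.108.

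- at 0.0125, z = 2.2414: exp(−0.1940) = 0.824 (Table 1 prints 0.823)
- at 0.01063, z = 2.3034: exp(−0.1994) = 0.819 (the Section 12 tables print 0.819)

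**Step 6: stated power.** With delayed effect, Table 1 case 3 gives 86.1% for a single analysis at 0.0125. The Section 12 table, for the full sequential plan ending at 0.01063, gives a cumulative 0.8388. That is 86.1 − 83.88 = 2.2 points lower, and below the 85% or greater promised in SAP 4.1.4 and 4.1.5, the protocol synopsis and protocol 9.5.

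**The case against.** The strongest reply is that Section 12 plainly governs. It is the specific text on the sequential plan, it covers the final look as well as the interims, and it states "with the adjusted final analysis to use 0.01063". Its simulated null rejection rates by the last look (0.0127 and 0.0119) are consistent with 0.0125. Protocol 9.8 agrees, and it entered in protocol Amendment 7, whereas this SAP version was written for Amendment 6. SAP 4.4 records that interim analysis was added, so 8.2.2 may simply not have been updated. On this reading the error limits hold.

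Most of this stands. A reader might infer that the trial as planned exceeds 0.025. The documents do not support that: the excess arises only if 8.2.2 is applied over Section 12 and protocol 9.8. What does not stand is that nothing needs changing, because neither document sets an order of precedence and 8.2.2 is the section that carries the test and its decision rule.

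Two further inferences should be resisted. One is that the 0.823 in Table 1 is an error. Table 1 is a single-analysis sizing simulation with its level declared, and 0.823 is right for that level. Putting 0.819 there would mix a sequential threshold with power and error columns simulated at 0.0125. The other is that the planned 95% confidence interval is part of this defect. At 534 deaths it excludes 1 for hazard ratios up to about 0.844, but most of the gap to the test threshold comes from the Bonferroni split (0.824 to 0.844 even without interim looks). SAP 8.2.2 also gives a reason for choosing 95%, namely comparability with other prostate cancer studies. That is a separate reporting question.

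**Conclusion.** The concern holds as an unreconciled contradiction over the primary success criterion: 0.0125 in SAP 8.2.2 against 0.01063 in SAP Section 12 and protocol 9.8, for the same test at 534 deaths. The Section 12 design itself is correct and reproduces exactly.

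If 8.2.2 were followed, type I error would be 0.0141 per comparison (limit 0.0125) and about 0.026 family-wise (Bonferroni bound 0.0283; limit 0.025). The excess is modest, and only a final hazard ratio between about 0.819 and 0.824 would change the conclusion. It still has to be settled before unblinding, because this is the decision rule of a pivotal trial.

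The figures assume the usual normal approximation for the logrank statistic, looks at the planned death counts, and, for the family-wise figure, both comparisons at the same information fractions with correlation 0.5.

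**What to change.** - **SAP 8.2.2:** replace the 0.0125 criterion with the Section 12 levels: 0.000135, 0.00147 and 0.00501 at the interim analyses and 0.01063 at the final analysis. Make the reference in SAP 8.2 to a previously specified criterion point to Section 12.
- **Table 1 (SAP 4.1.5):** keep the figures. Label them as single-analysis results not adjusted for interim looks, and refer to the Section 12 tables for the sequential critical hazard ratio of 0.819.
- **Power statements:** align the 85% or greater in the SAP and protocol with the SAP's own sequential delayed-effect result of 83.88%.
- **SAP 8.3:** say which level applies to AWE. Its sensitivity is currently illustrated at 0.0125.

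These are text changes; they add no subjects, deaths or procedures. The price is a slightly stricter final threshold than 8.2.2 now states and a slightly lower stated power.
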